5. PLANNED ANALYSES

5.1. Interim Analyses

There are no formal interim analyses planned for this study, however since the study is an open label single arm study, analyses to evaluate safety and efficacy will continue during the study. There are no formal stopping rules included in the study.

5.2. Analyses for Data and Safety Monitoring Board (DSMB) Meetings

An independent DSMB will monitor the safety of the trial. Select Tables, Figures and Listings will be generated and provided to the DSMB. Additional details of the list of tables, figures and listings (TFLs) will be agreed to with the DSMB and included in the DSMB Charter. A separate document will provide the mock shells of these TFLs to the DSMB. The schedule of the DSMB meetings will be detailed in the DSMB charter. Currently the first data meeting of the DSMB is planned when 50% (10) subjects complete one month after the first treatment. Any serious AEs are reported to the DSMB on a monthly basis, except deaths which will be reported as the sponsor is made aware of them.

The DSMB charter will also detail what will be provided to the DSMB on a monthly basis.

5.3. Final Analyses

Final analysis will be performed after database lock.

6. GENERAL CONSIDERATIONS FOR DATA ANALYSES AND HANDLING

This section addresses the definitions, algorithms, imputations, and conventions that will apply to the analysis and handling of the data in general. Rules that are data specific will be addressed in the detailed discussions of individual summary tables.

This SAP and all TFLs created will use U.S. spellings.

6.1. General Summary Table and Individual Subject Data Listing Considerations

Summary tables and listings (e.g., post text tables and individual subject data listings are prepared according to ICH Guideline E3) include a “footer” providing explanatory notes that indicate as a minimum:

1. Date of data extraction.
2. Date and time of output generation.
3. SAS program name, including the folder that generates the output. The full path may be replaced by a partial path before final run if requested by sponsor.
4. Any other output specific details that require further elaboration.

Summary tables will also include reference(s) to the subject data listing(s) that support the summary data.

Post text tables also include reference(s) to the subject data listing(s) that supports the summary data. The data extraction date links the output to the archived database that is frozen to ensure the replication of the results.

All Tables will display Treatment in one group labeled as “NurOwn®”.

Row entries in post text tables are always displayed for every category even if no data exists for any subjects (e.g., a row with all zeros will appear).

The summary tables will clearly indicate the number of subjects to which the data apply along with an indication for the number of subjects with missing data.

Summary tables for medications are coded according to the standard World Health Organization Drug Standard Dictionary [WHODD] Version September 2018. AE verbatim (reported) terms are coded to preferred terms (PT) and body/organ systems using Medical Dictionary for Regulatory Activities Terminology (MedDRA) Version 21.1.

Individual subject data listings will include all demographic, background, safety and efficacy data collected in the study, except for data collected on ActiGraph's CPIW which will only include summary data for each day and during the T25W. Individual Subject Data Listings, as a minimum, are sorted by Subject ID and Visit (Week), where applicable.

When missing or partial dates are imputed, the listings will display both the missing or partial dates as well as the imputed dates.

Any data derived for analyses will also be included with the raw data in the listings and flagged as derived data.

6.2. General Post Text Summary Table and Individual Subject Data Listing Format Considerations

The default convention is to number tables and listings and will use a decimal system to reflect main levels of unique tables and listings and sub-levels of replicate tables and listings with two digits per level and not more than 2 decimal digits (e.g., Table XX.YY.ZZ).

1. The first level number will be consistent with the corresponding CSR appendix in which the tables or listings will appear. For example, the post text tables usually occupy Appendix 14 and the individual subject data listings are put in Appendix 16.2. All post text tables will have a main number level 14 and listings 16.2. The subject disposition table is usually first in the first section of the report and will be numbered Table 14.1.1. The supportive subject data listing would be Listing 16.1. A subset of disposition table by site would have the number Table 14.1.2, etc. No more than 4 decimal digits will be used in numbering Tables and Listings (e.g. 14.a.b.c.d).
2. Subject disposition, baseline and demographics Tables will appear as the second level number (Table 14.1 series). Efficacy will come next (14.2 series) followed by safety (table 14.3 series). Similar conventions will be applied to the subject data listings.
3. The title will be complete, accurate, and concise. The last line of the title will provide the analysis group being summarized (e.g., All Subjects, Safety Population, Modified Intent-to-Treat Population or Efficacy-Evaluable Population). If possible, the units of measurement for data contained in the table can appear in parentheses to conserve space in the body of the table. For example, the summary of vital signs title could read “Summary of Sitting and Standing Blood Pressure (mmHg) and Heart Rate (bpm).” Whether in the title or body of a table or listing, units must always be specified for all appropriate data.
4. When relevant, variables being summarized, and statistics reported will appear in the left most column of a table. The next columns will report the data from left to right for the investigational drug by doses and for all treated subjects, respectively.

The definition of all derived variables and decodes for coded data must appear either on the Table or Listing. Due to space limitations, tables and listings may require a page of notes as a one-time preface to the output.

Tables and Listings will be self-contained and all-important information to review the Table or Listing will either be in the titles or footnotes.

6.3. Data Management

Data from the study will be entered into Bioclinica electronic data capture (EDC) version 5.6, a validated electronic 21CFR Part 11 compliant database. Data review, coding, and logic, range, cross-form, and consistency checks will be performed to ensure quality of the data. Adverse events (AE) and medications will be coded using MedDRA version 21.1 and the WHODD September 2018, respectively.

Derived datasets will be created using (SAS®) software. Statistical programming and analyses will be performed using SAS® Version 9.4 or higher.

6.4. Data Presentation Conventions

Continuous variables (e.g. age) are summarized using descriptive statistics (the number of subjects with available data, the mean, standard deviation (SD), first quartile (Q1), median, third quartile (Q3), minimum and maximum).

Categorical variables (e.g. race) are summarized using counts and percentages. Percentages are calculated using the total subjects within the dose group (or dose group and relevant subgroup when appropriate) being presented.

The following conventions are applied to all data presentations and summaries.

- For continuous variables, all mean, first quartile (Q1), median and third quartile (Q3) values are formatted to one more decimal place than the measured value. Minimum and maximum values are presented with the same number of decimal places as the measured value. For measure of variation, e.g. SD, use two more decimal places than the measured value, unless numbers are in at least 100s and there are space constraints in which case 1 decimal place is fine.
- For categorical variables, the number and percentage of responses are presented in the form XX (XX.X%) where the percentage is in the parentheses.
- Date variables are formatted as DDMMYY for presentation. Time is formatted in military time as HH:MM for presentation.
- Wherever possible, data will be decimal aligned or left aligned or as appropriate to best display the data and column headers. Parenthesis will also be aligned appropriately for best display.
- Hypothesis testing to determine if changes from baseline were statistically significant and comparing these against matched historical controls will be performed and presented in select Tables either as post-text Tables or in the CSR depending upon availability of historical data. Similar additional analyses on the percentage of responders from the current study against matched historical controls may be included in the CSR. Subjects from a historical database will be selected by matching key screening or baseline characteristics.
- P-values, if applicable, will be presented to 3 decimal places. If the p-value is less than 0.001 then it will be presented as <0.001. If the rounded result is a value of 1.000, it will be displayed as >0.999.

The table and listing shells and table of contents provide the expected layout and titles of the tables, listings and figures.

Any changes to format, layout, titles, numbering, or any other minor deviation will not necessitate a revision to the SAP nor will it be considered a deviation from planned analyses. Only true differences in the analysis methods or data handling will necessitate such documentation.

The appropriate listings supporting the tables will be included and are not specified in the individual sections throughout the document.

6.5. Analysis Populations

6.5.1. Safety Population

All safety analyses will be conducted on the Safety Population, which is defined as all participants who were enrolled, and had at least one transplantation performed.

6.5.2. Modified Intent to Treat (mITT) Population

All efficacy analysis will be conducted on the mITT population, which is defined in this study as all participants who are in the safety population and have at least one T25FW or 9-HPT assessment post baseline.

6.5.3. Efficacy Evaluable (EE) population

All efficacy analysis will be conducted on the EE population, which is defined as a subset of the mITT population that receive all 3 treatments and do not have any important protocol deviations impacting efficacy evaluation. If EE population is same as mITT population, then only mITT population would be used for all efficacy analysis.

6.6. Baseline Definition

The baseline visit will be defined as the most recent assessment prior to receiving the first transplantation at Visit 3.

6.7. Derived and Transformed Data

6.7.1. Baseline Age

Due to data protection requirements only year of birth and age at time of signing consent will be captured on the eCRF and no computation of age will be necessary.

6.7.2. Study Day

If the date of interest (date of visit, date of start of transplant, date of AE, etc.) occurs on or after the first transplantation date then study day will be calculated as (date of interest – date of first transplantation) + 1. If the date of interest occurs prior to the first transplantation date, then study day will be calculated as (date of interest – date of first transplantation). Study Day 1 is the date of first transplantation. There is no study day 0.

6.7.3. Change from Baseline

Change from baseline is calculated as (post-baseline result – baseline result).

Percent change from baseline is calculated as (change from baseline/baseline result)*100 as long as baseline is non-zero. If baseline is 0, change from baseline is defined as missing.

If either the baseline or the post-baseline result is missing, the change from baseline and/or percentage change from baseline is set to missing as well.

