15.2.4. Expanded Disability Status Scale (EDSS, Kurtzke)

The EDSS is an objective approach to quantify the level of physical disability in MS. It provides a total score on a scale that ranges from 0 (no disability) through 1 to 10 (death due to MS) in 0.5-point steps. The first levels 1.0 to 4.5 refer to people with a high degree of ambulatory ability and the subsequent levels 5.0 to 9.5 refer to the loss of ambulatory ability.

In addition, it also provides eight subscale measurements called Functional System (FS) scores. The levels of function within each category refer to the eight functional systems affected by MS: Pyramidal (motor function) (P); Cerebellar (C11); Brainstem (BS); Sensory (S); Bowel and Bladder (BB); Visual (V); Cerebral or Mental (Cb); Ambulation.

Administration time will vary depending upon the condition of the patient and the skill of the examiner. Although the FSS and EDSS themselves can be rated in a few minutes, the neurological examination that is needed to make the ratings can take anywhere from 15 minutes to a half-hour.

Table 3. Kurtzke Expanded Disability Status Scale (EDSS)

0.0	Normal neurological exam (all grade 0 in all Functional System (FS) scores*).
1.0	No disability, minimal signs in one FS* (i.e., grade 1).
1.5	No disability, minimal signs in more than one FS* (more than 1 FS grade 1).
2.0	Minimal disability in one FS (one FS grade 2, others 0 or 1).
2.5	Minimal disability in two FS (two FS grade 2, others 0 or 1).
3.0	Moderate disability in one FS (one FS grade 3, others 0 or 1) or mild disability in three or four FS (three or four FS grade 2, others 0 or 1) though fully ambulatory.
3.5	Fully ambulatory but with moderate disability in one FS (one grade 3) and one or two FS grade 2; or two FS grade 3 (others 0 or 1) or five grade 2 (others 0 or 1).
4.0	Fully ambulatory without aid, self-sufficient, up and about some 12 hours a day despite relatively severe disability consisting of one FS grade 4 (others 0 or 1), or combination of lesser grades exceeding limits of previous steps; able to walk without aid or rest greater than 500 meters.

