3.2.2. Secondary Endpoints

Secondary endpoints for the study are efficacy endpoints with the primary efficacy endpoint evaluated as indicated below:

- Percentage of subjects with improvement from baseline to Week 28 in either T25FW or 9-HPT of $\geq 25\%$.

[Section 9.6](#) provides additional details.

Other secondary efficacy endpoints evaluated include changes from baseline to each post baseline timepoint:

- Percentage of subjects who improve on T25FW by $\geq 25\%$ (Other thresholds such as $\geq 15\%$, $\geq 20\%$ and $\geq 30\%$ will also be evaluated)

BrainStorm Cell Therapeutics Ltd.
Statistical Analysis Plan - Protocol BCT-101-US

April 12, 2019

- Percentage of subjects who improve on 9-HPT by $\geq 25\%$ (Other thresholds such as $\geq 15\%$, $\geq 20\%$ and $\geq 30\%$ will also be evaluated)
- Mean Changes and % Changes in T25FW (ft/sec.)
- Mean Changes and % Changes in 9-HPT (sec.)
- Mean Changes and % Changes in various CSF and blood biomarkers (Biomarkers detailed below)
- Mean Changes and % Changes in EDSS Scores
- Mean Changes and % Changes in EDSS and its Functional System (FS) subscales (Pyramidal, Cerebellar, Brainstem, Sensory, Bowel and Bladder, Visual, Cerebral or Mental, and Ambulation)
- Percentage of Subjects that improve on EDSS by ≥ 1.0 for those with baseline EDSS ≤ 5.5 and improvement ≥ 0.5 for those with baseline EDSS > 5.5 (Note maximum EDSS for subjects enrolled is 6.5 inclusive)
- Mean Changes and % Changes in MSWS-12 Scores
- Percentage of Subjects that improve on MSWS-12 Scores by ≥ 8 points (other thresholds such as improvements of ≥ 7 , ≥ 9 points will also be evaluated)
- Mean Changes and % Changes in Daily Step Count as measured by CPIW
- Mean Changes and % Changes in Step Count as measured by CPIW during T25FW
- Mean Changes and % Changes in count per minute of daily activity as measured by CPIW
- Shift Table on time spent in each of the following categories: (Sedentary, Light, Lifestyle, Moderate, Vigorous, Very Vigorous) as measured by CPIW
- Percentage of time spent in light to vigorous physical activity based on a threshold of > 100 activity counts per minute as measured by CPIW
- Mean Changes and % Changes in LCLA Scores
- Percentage of subjects with an increase in LCLA score by ≥ 7 points (other thresholds such as improvements of ≥ 6 , ≥ 8 points will also be evaluated)
- Mean Changes and % Changes in SDMT Scores

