8.7. MRI analysis

MRI Data will be analyzed for safety by looking at the following change from baseline to end of study:

- Mean Changes in number of new or enlarging FLAIR lesions on MRI
- Percentage of subjects with $\geq 1, \geq 2, \geq 3$ new or enlarging FLAIR lesions on MRI
- Mean Changes in active FLAIR lesions (new + enlarging) on MRI
- Percentage of subjects with $\geq 1, \geq 2, \geq 3$ active FLAIR lesions (new + enlarging) on MRI
- Mean Change in Total volume of new FLAIR lesions on MRI
- Mean Change in Total volume of FLAIR lesions on MRI

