A daily assessment will be considered valid if the device was worn for at least 4 hours. Data from valid days of assessments will be scaled by taking the level of activity, dividing it by the number of hours the device was worn while awake and multiplying it by 16 (average waking period).

- Analyses will summarize mean changes and % changes and other descriptive statistics for continuous variables from baseline to each post baseline week in Daily step count averaged over valid data during 7 days as indicated above
- Count per minute of daily activity averaged over valid data during 7 days as indicated above

Mean changes and % changes and other descriptive statistics for continuous variables in Daily Step Count from baseline to each successive T25FW

Improvements will also be evaluated by the following categorical analyses:

- Shift Table on time spent in each of the following categories: (Sedentary, Light, Lifestyle, Moderate, Vigorous, Very Vigorous)
- Percentage of time spent in light to vigorous physical activity based on a threshold of > 100 activity counts per minute

Additional analyses using data collected and derived from the Center Point Insight Watch including improvements in sleep quality may be performed.

Low Contrast Letter Acuity (LCLA)

Mean Changes and % Changes from baseline to each post baseline timepoint in LCLA Scores will be summarized along with other descriptive statistics for continuous variables. The LCLA score is an integer between 0 and 70 and indicates the correct number of letters identified.

The scores are recorded for the right eye, left eye and both eyes combined. These will be analyzed for the three settings 100%, 2.5% and 1.5%.

Additional categorical analyses will summarize the number and percentage of subjects with an improvement (increase) in LCLA score by ≥ 7 letters. A 7 letter change in LCLA is considered clinically meaningful⁸. Other thresholds such as improvements of ≥ 6 , ≥ 8 letters will also be presented.

Sloan LCLA charts are administered binocularly or each eye can be tested individually. The charts are placed on a retro-illuminated cabinet, eliminating the need for standardized room lighting, or on the wall in front of the participant. Participants are seated 2 m away and asked to read the letters aloud proceeding top to bottom and from left to right until they can no longer see the letters.

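### SAP 6.7.3 contradicts itself on a zero baseline: as written it discards the absolute change, where only the percent change is undefined

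*SAP*

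**What the plan says.** SAP 6.7.3 contains four statements:

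- Change from baseline is the post-baseline result minus the baseline result, with no condition on the baseline value.
- "Percent change from baseline is calculated as (change from baseline/baseline result)*100 as long as baseline is non-zero".
- Directly after that, in the same paragraph: "If baseline is 0, change from baseline is defined as missing".
- The next paragraph deals with a missing baseline or post-baseline result. In that case "the change from baseline and/or percentage change from baseline is set to missing as well".

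SAP 6.8 imputes nothing except dates. Appendix I corrects other items in the SAP, for example the uric acid unit (Appendix I, 4.2), but leaves this sentence alone.

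Three planned analyses use mean change on a scale where 0 is a normal value:

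- **FS subscales.** SAP 3.2.2 lists "Mean Changes and % Changes in EDSS and its Functional System (FS) subscales".
- **LCLA.** SAP 9.6 plans mean changes for right eye, left eye and both eyes at three contrast settings. "The LCLA score is an integer between 0 and 70 and indicates the correct number of letters identified".
- **MRI.** SAP 8.7 plans, as a change from baseline to end of study, "Mean Changes in number of new or enlarging FLAIR lesions on MRI". MRI data are part of the primary safety endpoint (SAP 3.2.1), and Appendix I, 5.4 adds MRI to the efficacy analyses.

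**The concern.** Subtraction works at a baseline of 0; only division fails. The non-zero condition attached to percent change already deals with the division. The extra sentence is therefore either redundant or it deletes valid data. The following paragraph names change and percentage change as two separate quantities, so the SAP is not using one term for both. A programmer working literally would set both to missing.

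The patients lost would not be a random subset. An FS score of 0 can only stay or worsen, and an LCLA score of 0 can only stay or improve. Removing zero baselines removes patients who could move in only one direction and keeps those who had room to move in the other. With 20 patients, losing several from a mean is a visible share of the data, and the study's stated use is to inform a later randomised trial.

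**Working it through.** The plan gives no figure to reproduce, and the documents give no baseline distributions. The numbers below are illustrations under stated assumptions.

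**Can 0 occur at baseline?** Yes for FS scores. Entry requires EDSS 3.0 to 6.5 (Protocol 3.1), and Protocol Table 3 describes one form of EDSS 3.0 as a single functional system at grade 3 with the rest at 0 or 1. LCLA starts at 0 by definition.

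**Single patient.** FS 0 at baseline and 2 later. The subtraction gives 2 - 0 = +2. The disputed sentence gives missing.

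**General formula.** Let N be all patients, k those with baseline 0, d the mean change in those k, and m the mean change in the other N - k.

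- Full mean = [(N - k)m + kd] / N
- Literal mean = m, on N - k patients
- Literal minus full = (k/N)(m - d)

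On FS scores d cannot be negative. The artefact points towards improvement whenever m < d, and the other way when m > d.

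**FS cases, N = 20 (k, m and d assumed).**

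| k | m | d | Literal mean (n) | Full mean | Literal - full |
|---|---|---|---|---|---|
| 8 | 0 | 0.25 | 0.00 (12) | (0 + 2)/20 = +0.10 | -0.10 |
| 8 | -3/12 | 3/8 | -0.25 (12) | (-3 + 3)/20 = 0.00 | -0.25 |
| 16 | -0.25 | 0.50 | -0.25 (4) | (-1 + 8)/20 = +0.35 | -0.60 |
| 16 | +0.25 | 0 | +0.25 (4) | (1 + 0)/20 = +0.05 | +0.20 |

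The last two rows are the extremes of a grid with k from 4 to 16, 0 to 50% of zero-baseline patients worsening by one grade, and m from -0.25 to +0.25.

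**No true change, scoring error only.** Assume true grades 0/1/2/3 in 40/25/20/15% of patients. At each visit the score is one grade too high with probability e and one grade too low with probability e, with a floor at 0. Then:

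- Share with observed baseline 0: p0 = 0.40(1 - e) + 0.25e
- Summed change in that group, per patient enrolled: S = 0.40(1 - e)e + 0.25e
- The mean over all patients is 0, so the retained mean is -S/(1 - p0)

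| e | p0 | S | Retained mean |
|---|---|---|---|
| 0.05 | 0.3925 | 0.0315 | -0.0315/0.6075 = -0.05 |
| 0.15 | 0.3775 | 0.0885 | -0.0885/0.6225 = -0.14 |
| 0.20 | 0.3700 | 0.1140 | -0.1140/0.6300 = -0.18 |

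**LCLA.** Suppose one of 20 patients goes from 0 to 10 letters on one chart and the others do not change. The full mean is 10/20 = +0.5 letters. The literal mean is 0.0 on 19 patients, so here the loss works against the product.

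**MRI.** Scans are scheduled only at Visits 1 and 7. A count of new lesions at Visit 1 needs an earlier reference scan, and the SAP defines none.

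- If the Visit 1 count is 0 by construction, k = 20 and the literal rule leaves no patients in that mean. If 20% gained one lesion, the full mean would be 4/20 = +0.2.
- If some earlier scan were used, and the other patients went from 2 lesions to 1, then k = 10 gives -1.0 literal against (2 - 10)/20 = -0.4, and k = 15 gives -1.0 against (3 - 5)/20 = -0.1.

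**The case against.** The strongest reply is that this is a dropped word. The sentence sits in the percent-change paragraph, immediately after the non-zero condition, and conflicts with the unrestricted definition that opens the section. Read in place it is a zero-denominator rule and does no harm. That is probably what was meant, and it stands as an explanation. It does not remove the contradiction, and nothing in the SAP or Appendix I tells a programmer which reading to use.

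The second reply is that other outputs would still show these patients. That also stands:

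- SAP 9.6 presents FS changes as a shift table, which needs no subtraction.
- SAP 8.7 plans percentages with at least 1, 2 or 3 new or enlarging lesions, which can be counted directly.
- Total EDSS is kept away from 0 by the entry range.
- T25FW and 9-HPT cannot have a true zero baseline, so the primary efficacy endpoint is safe.
- The LCLA responder rule can be computed from the scores, and is exposed only if the program takes it from the derived change variable.
- Individual data appear in the listings (SAP 6.1).

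A reader might infer that the plan removes patients who worsened and so makes stable disease look like improvement. The documents do not support that. The rule would remove all zero-baseline patients, stable ones included. The direction depends on the retained patients and is opposite on LCLA. Nor do the documents show that the literal reading was ever programmed. For new-lesion counts the likelier failure is an empty table, which would be noticed, and not a hidden bias.

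**Conclusion.** SAP 6.7.3 is wrong as written and should be corrected. The contradiction is certain; the consequence is conditional on the programming.

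Under the literal reading, the mean absolute changes for FS subscales and LCLA lose every zero-baseline patient, and the new-lesion mean may lose everyone. For FS scores with no true change, the artefact is about -0.05 to -0.18 grade under the assumed grade mix and error rates. Across the wider grid of assumed values it runs from -0.60 to +0.20. None of these distributions comes from the documents, so they show what is possible and do not predict the result.

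This is a wording correction to be verified against the programs. It does not touch the T25FW/9-HPT responder analysis.

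**What to change.** 1. In SAP 6.7.3, replace the sentence with: *If baseline is 0, percent change from baseline is defined as missing; change from baseline is still calculated.*
2. Check the derivation programs for FS scores, LCLA and MRI against that sentence. If the literal rule was coded, rerun the affected means and confirm that each n matches the number of patients with both values.
3. In SAP 8.7, report the number and volume of new or enlarging FLAIR lesions on the Visit 7 scan relative to the Visit 1 scan, with no subtraction of a baseline new-lesion value. Total FLAIR volume can stay as a change from baseline.

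The cost is one sentence in 6.7.3, a wording change in 8.7 and a short program check. No new data are needed.
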